20.4 Criteria for Suspending/Terminating a Study Site

Boston Scientific reserves the right to stop the inclusion of subjects at a study site at any time after the study initiation visit if no subjects have been enrolled for a period beyond 6 months after site initiation, or if the site has multiple or severe protocol violations/noncompliance without justification and/or fails to follow remedial actions.

In the event of termination of site participation, all devices and testing equipment (Sponsor Equipment), as applicable, will be returned to BSC unless this action would jeopardize the rights, safety or well-being of the subjects. The IRB/EC and regulatory authorities, as applicable, will be notified. Study participants will be contacted, as applicable, and be informed of changes to study visit schedule.

21. Study Registration and Results

21.1. Study Registration

To comply with applicable laws and regulations, the study will be registered on a publicly accessible database.

21.2. Clinical Investigation Report

Study results will be made available in accordance with the legal requirements and the recognized ethical principles, in accordance with the Boston Scientific Policy. A Clinical Investigation Report will be made available to all investigators, IRB/EC and regulatory authorities, as applicable in accordance with the Boston Scientific Policy and local requirements. As applicable an abbreviated Clinical Investigation Report will be made available on a publicly accessible database.

21.3. Publication Policy

BSC requires disclosure of its involvement as a sponsor or financial supporter in any publication or presentation relating to a BSC study or its results. BSC may submit study results for publication (regardless of study outcome) following the conclusion or termination of the study. Boston Scientific adheres to the Contributorship Criteria set forth in the Uniform Requirements of the International Committee of Medical Journal Editors (ICMJE; <http://www.icmje.org>). In order to ensure the public disclosure of study results in a timely manner, while maintaining an unbiased presentation of study outcomes, BSC personnel may assist authors and investigators in publication preparation provided the following guidelines are followed:

- All authorship and contributorship requirements as described above must be followed.

- BSC involvement in the publication preparation and the BSC Publication Policy should be discussed with the Coordinating Principal Investigator(s) and/or Executive/Steering Committee at the onset of the project.
- The First and Senior authors are the primary drivers of decisions regarding publication content, review, approval, and submission.

The data, analytic methods, and study materials for this clinical trial may be made available to other researchers in accordance with the Boston Scientific Data Sharing Policy (<https://www.bostonscientific.com/>).

22. Bibliography

23.1. Abbreviations

Abbreviations are shown in Table 23.1-1Table 23.1-1.

Table 23.1-1: Abbreviations

Abbreviation/Acronym	Term
AAD	Anti-Arrhythmic Drugs
ACT	Activated Clotting Time
ADE	Adverse Device Effect

Table 23.1-1: Abbreviations

Abbreviation/Acronym	Term
AE	Adverse Event
AF	Atrial Fibrillation
AF-CB4	Fourth Generation of Arctic Front Cryoballoon
AFEQT	Atrial Fibrillation Effect on Quality of Life Survey
AFL	Atrial Flutter
AT	Atrial Tachycardia
CABG	Coronary artery bypass grafting
CRT	Cardiac Resynchronization Therapy
CS	Coronary Sinus
CTI	Cavotricuspid Isthmus
CVA	Cerebrovascular Accident
DD	Device Deficiency
DMS	Diaphragm Movement Sensor
DVT	Deep Vein Thrombosis
EC	Ethics Committee
ECG	Electrocardiogram
eCRF	Electronic Case Report Form
EDC	Electronic Data Capture
EP	Electrophysiology
ESC	European Society of Cardiology
HCP	Health Care Personnel
ICB	Inter Connection Box
ICE	Intracardiac Echo
ICF	Informed Consent Form
IFU	Instructions for Use
JCS	Japan Circulation Society
JHRS	Japan Heart Rhythm Society
LA	Left Atrium
LAAO	Left Atrial Appendage Occlusion
MI	Myocardial Infarction
MRI	Magnetic Resonance Imaging
N ₂ O	Nitrogen Dioxides
PCI	Percutaneous Coronary Intervention
PM	Pacemaker
PMCF	Post Market Clinical Follow-up
PTCA	Percutaneous transluminal coronary angioplasty
PV	Pulmonary Vein
PVI	Pulmonary Vein Isolation
RA	Right Atrium
SADE	Serious Adverse Device Effect
SAE	Serious Adverse Event
TEE	Trans-esophageal echocardiography
TIA	Transient Ischemic Attack
TSF	Technical Source Form

Table 23.1-1: Abbreviations

Abbreviation/Acronym	Term
TTE	Trans-Thoracic echocardiography
TTI	Time-to-isolation
UADE	Unanticipated Adverse Device Effect
USADE	Unanticipated Serious Adverse Device Effect

23.2. Definitions

Terms are defined in Table 23.2-1: Definition.

Table 23.2-1: Definition

Term	Definition
Activated Coagulation/Clotting Time	ACT is a test that is used to monitor the effectiveness of high dose heparin therapy.
Arterial-Venous Fistula	Abnormal communication between an artery and a vein.
Atrioesophageal Fistula	A connection between the atrium and the lumen of the esophagus.
Attempt Subject	Any subject that signs the consent form, and has any study device inserted into the body but does not receive any Cryoablation application.
AV block	A conduction disturbance that results in the partial inability of an electrical impulse generated in the atria to reach the ventricles.
Blanking Period	90-day period between ablation procedure and the initiation of the Effectiveness Evaluation Period during which up to one additional ablation procedure can be performed and subjects can be prescribed antiarrhythmic drugs as determined necessary by the investigator.
Cardiac tamponade/perforation	The development of a significant pericardial effusion during or within 30 days of undergoing an AF ablation procedure. A significant pericardial effusion is one that results in hemodynamic compromise, requires elective or urgent pericardiocentesis, or results in a 1-cm or more pericardial effusion as documented by echocardiography.
Embolism	The sudden blocking of an artery by a clot or foreign material which has been brought to its site of lodgment by the blood current.
Enrolled Subject	A subject who has given written informed consent to participate in the study.
Hematoma	A localized collection of blood, usually clotted, in an organ, space or tissue, due to a break in the wall of a blood vessel.
Intent Subject	Any subject that signs the consent form but does not have any study devices inserted into the body. Subjects who are enrolled in the study but do not undergo ablation procedure within 90 days from consent signature date may not be reconsented and will be withdrawn from the study.
In-patient Hospitalization	Hospitalizations ≥ 24 hours in duration or < 24 hours with medical intravenous therapy or surgical intervention

Table 23.2-1: Definition

Term	Definition
Myocardial infarction (in the context of AF ablation)	
The presence of any one of the following criteria:
 
(1) detection of ECG changes indicative of new ischemia (new STT wave changes or new LBBB) that persist for more than 1 hour;
 
(2) development of new pathological Q waves on an ECG;
 
(3) imaging evidence of new loss of viable myocardium or new regional wall motion abnormality

Occlusion Grade	
Score 4 = excellent (full retention of contrast medium without visible outflow)
 
Score 3 = moderate (incomplete occlusion with slight leakage of contrast medium)
 
Score 2 = poor (presence of sustained and massive leakage of contrast medium)
 
Score 1 = very poor (immediate rapid outflow from the PV).

Paroxysmal Atrial Fibrillation	Recurrent symptomatic Atrial Fibrillation that terminates spontaneously or with intervention within seven days of onset.
Pericardial Effusion	A collection of fluid or blood in the pericardial space around the heart or in pleural space around the lungs.
Pericarditis	Inflammation of the pericardium surrounding the heart. Pericarditis should be considered a major complication following ablation if it results in an effusion that leads to hemodynamic compromise or requires pericardiocentesis, prolongs hospitalization by more than 48 hours, requires hospitalization, or persists for more than 30 days following the ablation procedure.
Pneumothorax	Collapse of the lung due to an abrupt change in the intrapleural pressure within the chest cavity.
Primary Effectiveness Failure	
A TREATMENT subject with
 
 • Acute procedure failure • Documented atrial fibrillation, or new onset of atrial flutter or atrial tachycardia event (≥ 30 seconds in duration from an event monitor or Holter, or from a 10 second 12-lead ECG) between Days 91 and 12-month post index procedure • Any of the following interventions for atrial fibrillation, or new onset of atrial flutter or atrial tachycardia between Days 91 and 12-month post index procedure: 
 ○ Repeat AF procedure ○ Electrical and/or pharmacological cardioversion for AF/AFL/AT ○ Prescribed a higher dose of any AAD documented at baseline or a new AAD not documented at baseline
Procedural Success	Pulmonary vein isolation achieved with the Boston Scientific cryoablation system as demonstrated by entrance block at the minimum.
Prolonged Hospitalization	Hospitalization ≥ 72 hours after the study procedure for reasons other than anticoagulation
Pseudoaneurysm	A dilation of an artery with disruption of one or more layers of its walls.

Table 23.2-1: Definition

Term	Definition
Pulmonary Edema/Heart Failure	Ineffective pumping of the heart leading to an accumulation of fluid in the lungs. Typical symptoms include shortness of breath with exertion, difficulty breathing when lying flat and leg or ankle swelling.
Pulmonary Vein Stenosis (Significant)	Pulmonary vein stenosis is defined as a reduction of the diameter of a PV or PV branch. For the primary safety endpoint of this study, significant pulmonary vein stenosis is defined as symptomatic and requiring intervention.
Source Data Ref: ISO 14155	All information in original records, certified copies of original records of clinical findings, observations, or other activities in a clinical investigation, necessary for the reconstruction and evaluation of the clinical investigation. This includes source data initially recorded in an electronic format.
Source Document	Printed, optical or electronic document containing source data. Examples: Hospital records, laboratory notes, device accountability records, radiographs, records kept at the investigation site, and at the laboratories involved in the clinical study.
Stroke/Cerebrovascular accident (CVA)	
Rapid onset of a focal or global neurological deficit with at least one of the following: change in level of consciousness, hemiplegia, hemiparesis, numbness or sensory loss affecting one side of the body, dysphasia or aphasia, hemianopia, amaurosis fugax, or other neurological signs or symptoms consistent with stroke.
 
Duration of a focal or global neurological deficit \geq24 hours; OR $<$24 hours if therapeutic intervention(s) were performed (e.g., thrombolytic therapy or intracranial angioplasty); OR available neuroimaging documents a new hemorrhage or infarct; OR the neurological deficit results in death.
 
No other readily identifiable non-stroke cause for the clinical presentation (e.g., brain tumor, trauma, infection, hypoglycemia, peripheral lesion, pharmacological influences).
 
Confirmation of the diagnosis by at least one of the following: neurology or neurosurgical specialist; neuroimaging procedure (MRI or CT scan or cerebral angiography); lumbar puncture (i.e., spinal fluid analysis diagnostic of intracranial hemorrhage).

Symptomatic AF	Required symptom(s) of AF that were experienced by the subject, made them seek medical attention, and were concurrent with a documented episode by ECG, event monitoring and/or Holter monitor. Symptoms may have included palpitations, irregular pulse (i.e. rapid, racing, pounding, fluttering, bradycardic), dizziness, weakness, chest discomfort, and breathlessness.
Thrombus	An aggregation of blood factors, primarily platelets and fibrin with entrapment of cellular elements, frequently causing vascular obstruction at the point of its formation.
Thromboembolism	The blockage of a blood vessel lumen by air or solid material such as device fragments, blood clot or other tissues that have migrated from another anatomic site.
Transient Ischemic Attack (TIA)	New focal neurological deficit with rapid symptom resolution (usually 1 to 2 hours), always within 24 hours; neuroimaging without tissue injury

Table 23.2-1: Definition

Term	Definition
Treatment Subject	Any subject that signs the consent form, and has the specified study devices inserted into the body and undergoes protocol specific treatment (cryoablation) for the intended disease.
Vagal Nerve Injury/Gastroparesis	Vagal nerve injury is defined as injury to the vagal nerve that results in esophageal dysmotility or gastroparesis. Vagal nerve injury is considered to be a major complication if it prolongs hospitalization, requires hospitalization, or results in ongoing symptoms for more than 30 days following an ablation procedure
Vascular access complications	Development of a hematoma, an AV fistula, or a pseudoaneurysm. A major vascular complication is defined as one that requires intervention, such as surgical repair or transfusion, prolongs the hospital stay, or requires hospital admission.

24. Appendices

24.1. *Quality of Life Instruments*

Clinical trials increasingly recognize the value of including patient reported outcome measures in their design. To understand the impact of atrial fibrillation ablation procedures on subject's quality of life, the quality of life instruments used for this study will be the EQ-5D-5L for a generic questionnaire and the AFEQT for disease specific. Subjects will be asked to complete the questionnaires at the Enrollment visit and 12- month close out follow-up.

The EQ-5D, generic quality of life measure, will be used to assess health utilities. It is a descriptive system of health-related quality of life states consisting of five dimensions (mobility, self-care, usual activities, pain/discomfort, anxiety/depression) each of which can take one of five responses. The responses record five levels of severity (no problems/ slight problems/ moderate problems/ severe problems/ extreme problems) within a particular EQ-5D dimension.

The Atrial Fibrillation Effect on Quality of Life Survey (AFEQT) was developed to evaluate disease specific quality of life for patients with atrial fibrillation. The 20-item questionnaire is subdivided into three domains: symptoms, daily activities, and treatment concerns with responses provided on a seven-point Likert scale.

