6.2. Study Endpoints

6.2.1. Primary Safety Endpoint

The primary safety endpoint will be evaluated by the safety event free rate at 12 months post-index procedure.

Primary safety events will consist of a composite of the following procedure-related and device-related adverse events.

Acute primary safety endpoint events, events occurring up to 7 days post-index procedure or hospital discharge, whichever is later, include:

- Death
- Myocardial infarction (MI)
- Gastroparesis / injury to vagus nerve
- Transient ischemic attack (TIA)
- Stroke / Cerebrovascular accident (CVA)
- Thromboembolism / Air embolism*
- Cardiac tamponade / perforation
- Pneumothorax
- Serious vascular access complications**
- Pulmonary edema / heart failure
- AV block not attributable to medication effect or vasovagal reaction

* Thromboembolic or air embolic events collected in the study refer to any occlusion of blood vessel(s) that results in clinical symptoms.

** Defined as prolongation of hospitalization, requirement of surgical intervention or blood transfusion.

Chronic primary safety endpoint events, events occurring through 12 months post-index procedure, include:

- Atrial esophageal fistula
- Significant PV stenosis ($\geq 70\%$ reduction of diameter of the PV from baseline*** **OR** presented by patient's symptoms at 12-Month follow-up and requiring intervention)
- Symptomatic pericardial effusion
- Persistent phrenic nerve injury****

*** Recommended to use the same imaging method as baseline.

**** A non-recovered phrenic nerve injury at 12 months post-index procedure will count as a chronic primary endpoint. The study will collect information on phrenic nerve palsy observed before the end of the index procedure and, in case it occurred, will track information for potential recovery during the study visits.

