To collect continued effectiveness data of the Cryoablation System	Failure-free rate at 12 months including: i. failure to achieve success at index procedure, ii. documented AF/AFL/AT iii. interventions to treat these arrhythmias after blanking period, including repeated procedures cardioversion or prescription of new anti-arrhythmic drugs (or higher dose)	
Secondary		
Acute procedural success	Success of procedure (PVI)	Component of the primary effectiveness endpoint
To collect continued effectiveness data of the Cryoablation System	Failure-free rate at 6 months including failure to achieve success at index procedure, documented AF/AFL/AT or interventions to treat these arrhythmias after blanking period, including repeated procedures cardioversion or prescription of new anti-rrhythmic drugs (or higher dose)	To determine potential early benefits comparing to 12 months that has been established by the HRS consensus document.
Additional		
Quality of life assessment	Changes in the quality of life measures (AFEQT and EQ-5D-5L) between baseline and 12 months follow up	Relief from symptoms is one of the main ouotcomes reported of AF ablation

7. Study Design

The POLAR SMART study is a prospective, multicenter, single arm, post-market study.

All subjects signing the consent, undergoing the index (ablation) procedure and treated with the study devices will be followed up for one year.

7.1. *Scale and Duration*

- A minimum sample size of 200 subjects treated only with PVI is required. The maximum overall study sample size will be limited to ≤ 400 subjects.
- To avoid any center effect and bias, individual centers will not be allowed to enroll more than 20 subjects meeting enrollment criteria, unless Boston Scientific gives written approval to do so. The enrollment period is approximately 12 months.
- Approximately 30 sites in Japan and South Korea.
- Total expectation duration of study with all follow-up data collected is estimated to be approximately 36 months.
- The study duration for each subject is expected to be approximately 12 months. Each subject will be followed up at:
 - Enrollment and Baseline clinic visit, baseline visit can be the same day as enrollment visit, however the Informed Consent must be signed and dated prior to conducting any study related activities (up to 90 days before Index Procedure);
 - Index (Ablation) procedure (day 0);
 - Pre-discharge visit must be done before hospital discharge (required);

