Imaging, per SOC at the site	Retain at Center
Documentation of new AF/AFL/AT AND Intervention for AF/AFL/AT	Retain at Center
Adverse Events	Retain at Center
In the event of a subject death (if requested):	

 • Death narrative • Relevant medical records • Death Certificate • Autopsy report 	Submit one copy to BSC, Retain one copy at center

11. Statistical Considerations

Statistical considerations for the primary and secondary endpoints are described in the following sections. Note that no formal hypothesis tests are planned for the endpoints.

11.1. *Endpoints*

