19.1. Safety Monitoring Process

The BSC personnel from the Medical Safety and Safety Trial Operation group review safety data as it is reported by the sites throughout the duration of the study. During scheduled monitoring activities, clinical research monitors further support this review through their review of source documents and other data information. The BSC Medical Safety and Safety Trial Operations team include health care providers with expertise in Electrophysiology and with the necessary therapeutic and subject matter expertise to evaluate and classify the events into the categories outlined above.

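### Read literally, the only definition of AV block (Table 23.2-1) covers partial failure of conduction and so leaves complete AV block out of a primary safety component

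*Combined protocol and SAP*

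**What the plan says.** The primary safety endpoint is a composite: "Primary safety events will consist of a composite of the following procedure-related and device-related adverse events". Its acute components are "events occurring up to 7 days post-index procedure or hospital discharge, whichever is later, include" a list that ends, in both section 6.2.1 and the synopsis, with "AV block not attributable to medication effect or vasovagal reaction". That line excludes two causes. It gives no degree, duration or severity, and no footnote is attached to it.

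Section 23.2 opens by stating "Terms are defined in Table 23.2-1: Definition". The table's entry for AV block is "A conduction disturbance that results in the partial inability of an electrical impulse generated in the atria to reach the ventricles".

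Under section 19.1, the sponsor's medical safety group reviews the reports "to evaluate and classify the events into the categories outlined above". The protocol gives no separate adjudication definition of AV block.

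**The concern.** The endpoint list uses an unqualified term, and the table that defines the terms narrows it to partial failure of conduction. A classifier who applies the table as written would accept a partial block and reject a complete one. A classifier who uses the ordinary meaning of the term would accept both. Two careful people could therefore code the same case differently, each with a defensible basis.

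This matters because the study has a single arm. Section 7.3 says adverse events will be compared with literature rates, and such a comparison depends on knowing exactly what was counted. If the rule is settled only when a case arises, it is settled with the outcome in view.

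**Working it through.** This is mainly a check of text. The plan states no figure to reproduce.

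**Step 1. Set the texts side by side.**

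| Place | What it says about AV block | Partial block | Complete block |
|---|---|---|---|
| Synopsis and 6.2.1 | Named without degree; two causes excluded | Counts | Counts |
| Table 23.2-1 | Partial failure of conduction only | Counts | Does not meet the definition |

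Both rows assume that the event is procedure- or device-related, falls in the acute window, and is not due to medication or a vasovagal reaction.

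**Step 2. Look for anything that restores complete block.** No other section defines or grades AV block, and none mentions complete or third-degree block. The table is the only definition.

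**Step 3. Ask whether the table bears on the endpoint.** Section 23.2 presents it as the place where terms are defined. Its entry for significant pulmonary vein stenosis refers expressly to the primary safety endpoint. The table therefore cannot be set aside as background.

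**Step 4. Ask whether the event would be lost altogether.** It would not. Section 17.1 requires reporting of all serious adverse events and of all procedure- or device-related events. Only the step from reported event to primary safety event is affected.

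**Step 5. Size of one uncounted case.** Inputs:
- The minimum number of PVI-only subjects is 200. Section 7.1: "A minimum sample size of 200 subjects treated only with PVI is required".
- The main analyses are limited to PVI-only subjects (11.2.1).
- Assumptions: no censoring, and no other primary safety event in the affected subject.

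Without censoring, the Kaplan-Meier event-free rate is 1 − d/n, where d is the number of subjects with an event. Leaving out one case changes it to 1 − (d − 1)/n, a rise of 1/n:

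- n = 200: 1/200 = 0.005, or 0.5 percentage points.
- n = 400, the ceiling for the whole study and so an upper bound for PVI-only subjects: 1/400 = 0.0025, or 0.25 percentage points.

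The documents give no expected rate of AV block or of the composite, so an expected total effect cannot be calculated. Section 11 adds: "Note that no formal hypothesis tests are planned for the endpoints". No alpha, power or margin depends on this point.

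**The case against.** The strongest reply is that the operative text is section 6.2.1, which is not limited to partial block and does not refer to the table. Where that section wants to qualify a component, it does so in the list or by footnote. Some table entries are loose descriptions: the one for pericardial effusion also mentions fluid in the pleural space. The classifiers include health care providers with electrophysiology expertise (19.1), who are unlikely to exclude complete block from a component called AV block.

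Much of this stands. The wording is probably an omission, and the practical risk is low. It does not remove the defect, because the classifier reaches the sensible result only by departing from the protocol's own definition.

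A reader might infer more than the documents support:

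- **That the sponsor chose to exclude the worse event, or that safety monitoring would miss it.** Nothing indicates intent, and section 17.1 still captures the event when it is serious or related. Whether a given case is serious depends on the criteria in Table 17.2-1. The documents do not rank degrees of block, and the point does not need such a ranking.
- **That right-atrial ablation in general exposes the main result.** Section 10.5.3 allows such ablation with another system. Section 9.4.4 keeps PVI plus CTI within PVI-only, but puts additional ablation intended to treat AF, AT or atypical AFL in PVI+. Only the CTI case clearly reaches the main analysis.
- **That the definition needs a severity threshold because a brief partial block can meet it.** Such a block must also be procedure- or device-related and not due to medication or a vasovagal reaction. No threshold appears in the documents, and closing the gap does not require one.

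**Conclusion.** The point holds as a defect of wording in one component of the primary safety endpoint. Followed literally, the only definition excludes complete AV block, while the endpoint list includes AV block without qualification. The consequence is limited to classification. Each uncounted case would raise the 12-month event-free rate by 0.5 percentage points at 200 PVI-only subjects, on the assumptions given above. A confidence interval for the shift would need event counts that the documents do not supply, so none is offered. No pass or fail decision turns on it. It is worth correcting because the endpoint is primary and the remedy is small, not because a large bias is expected.

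**What to change.** Change the AV block entry in Table 23.2-1 to refer to *partial or complete inability* of the impulse to reach the ventricles, so that it matches the unqualified term in section 6.2.1 and the synopsis. Do this before events are classified. Add no degree threshold and no separate line for blocks that resolve.

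The cost is one line of text. Because partial and complete block would both count, the rule needs no new data field, visit or subject. Section 14.3 requires ethics review of any protocol amendment, so the change is best carried with another one.
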